5.4.1 Primary Analysis for Phase 1b

The primary objective of Phase 1b is to determine the DLTs, MTD, and to establish the RP2D. The endpoint DLTs in Phase 1b will be summarized based on the MTD Analysis Set.

5.4.2 Primary Efficacy Analysis for Phase 2

The primary efficacy endpoint in Phase 2 is objective response rate as of Week 24 (ORR_(Week 24)) based on irRECIST. The primary efficacy analysis of ORR(Week 24) for each cohort may be performed based on the Full Analysis Set when all subjects in that cohort have completed 8 cycles of treatment, or discontinued early due to disease progression, unacceptable toxicity, consent withdrawn, or the study termination by the Sponsor. Estimated ORR_(Week 24) and the exact 95% confidence intervals using the method of Clopper–Pearson will be presented.

5.4.3 Secondary Efficacy Analyses for Both Phase 1b and Phase 2

The following secondary efficacy analyses will be performed.

Objective Response Rate (ORR): The ORR is the proportion of patients achieving a best overall response of confirmed PR or CR at the time of data cutoff. Subjects who do not have a tumor response assessment for any reason will be considered non-responders and will be included in the denominator when calculating the response rate. The count and percentage for the ORR will be summarized. ORR and corresponding 95% CI based on exact binomial distribution will be estimated for each treatment cohort.

Progression-Free Survival (PFS): The PFS is defined as the time from the first study dose date to the date of first documentation of confirmed PD using irRECIST or death (whichever occurs first). If a subject has not experienced disease progression or death, then the subject's

data will be censored at the date of the last adequate radiologic assessment. The PFS censoring rules in this SAP and definition of progression date follow the principles of the Food and Drug Administration (FDA) “[Guidance for Industry Clinical Trial Endpoints for the Approval of Cancer Drugs and Biologics \(2007\)](#)”. Due to the use of pembrolizumab, all tumor assessments up to the first PD identified under irRCIST are considered as long as the subjects did not start a new anti-cancer therapy. The date of radiological assessment is based on the date of scans performed for a time point. The date will be based on the time point required CT/MRI scans unless there is a new lesion on the bone scan(s) or brain scan(s) performed to ensure CR or PR, or on brain scan(s) performed to ensure CR. Table 5 shows the censoring rules for the derivation of PFS.

Table 5 Censoring rules for the derivation of PFS.

No.	Situation	Date of Event (Progression/Death) or Censoring	Outcome
1	No baseline tumor assessments	Date of first dose	Censored
2	Progression documented between scheduled visits	Date of first radiologic PD assessment	Event
3	No progression	Date of last adequate radiologic assessment	Censored
4	New anticancer treatment started	Date of last adequate radiologic assessment prior to or on date of new anticancer treatment	Censored
5	Death before first PD assessment	Date of death	Event
6	Death between adequate assessment visits*	Date of death	Event
7	Death or progression after more than one missed visit/tumor assessment**	Date of last adequate radiologic assessment before missed tumor assessments	Censored

CR = complete response, PD = progressive disease, PR = partial response, SD =stable disease,

* Adequate tumor assessment is radiologic assessment at regular interval as defined in the protocol.

** More than one missed visit/adequate tumor assessment is defined as having the duration between the last adequate tumor assessment and death or PD being longer than 14 weeks - 1 day, which is 97 days ($= ((6+1) \times 2 \times 7) - 1$) for subjects on the every 6 week tumor assessment schedule in the first 8 cycles of treatment and 20 weeks - 1 day, which is 139 days ($= ((9+1) \times 2 \times 7) - 1$) for subjects on the every 9 week tumor assessment schedule after Cycle 8 in this study.

The priority of the censoring rules is as follows,

1. If the subject had PD or death, the following sequence will be applied:

- If a subject did not have a baseline tumor assessment (No. 1), the subject will be censored on the

date of first dose.

- If the subject died within 97 days (14 weeks -1 day) following first dose and did not receive a new anticancer treatment, it will be counted as PFS event at the date of death.
- If a subject had new anticancer treatment before PD or death (No. 4), the subject will be censored on the date of the last adequate tumor assessment prior to or on the date of new anticancer treatment.
- If a subject missed two or more tumor assessments before PD or death (No. 7), the subject will be censored on the date of the last adequate tumor assessment before PD or death. Note that if a subject is censored by both this criterion and the anticancer treatment criterion, the earliest censoring date will be used.
- Otherwise, if a subject had an event (No. 2, No. 5, or No. 6), the earliest event date will be used.

2. If a subject did not have PD or death, the censoring date will be the earliest censoring date if the subject met multiple censoring criteria (No. 1, No. 3, No. 4, No. 7).

The distribution of PFS and time curve will be estimated using Kaplan–Meier method. Median time to PFS and 95% CI will be provided for each cohort. Three-month, 6-month, 9-month, and 12-month PFS rate will be estimated using the Kaplan–Meier method and corresponding 95% CIs will be provided.

Overall Survival (OS): OS is measured from the start date of the treatment phase until date of death from any cause. All events of death will be included, regardless of whether the event occurred while the subject was still taking study drug, or after the subject discontinued study drug. If a subject has no record of death, then the data will be censored at the date the subject was last known to be alive, or the data cutoff date, whichever is earlier (see Table 6 for censoring rules). The distribution of OS and time curve will be estimated using Kaplan–Meier method. Median survival time and the corresponding 95% CI, survival rates at 12, 18, and 24 months, and corresponding 95% CIs will be estimated using Kaplan–Meier method for each treatment cohort.

Table 6 Censoring Rules for Overall Survival Endpoint

Situation	Event Date or Censoring	Outcome
Death during study	Date of death	Death
Death after data cut-off	Date of data cut-off	Censored
Subject still alive at data cut-off	Date of data cut-off	Censored

Situation	Event Date or Censoring	Outcome
Subject lost to follow-up before data cut-off	Date last known to be alive	Censored

Disease Control Rate (DCR): The DCR is the proportion of subjects who have BOR of CR or PR or SD (minimum duration from C1D1 to SD ≥ 5 weeks). The count and percentage with exact 95% CI for the DCR will be summarized.

Clinical Benefit Rate (CBR): The CBR is the proportion of subjects who have BOR of CR or PR or durable SD (duration of SD ≥ 23 weeks). The count and percentage with exact 95% CI for the CBR will be summarized.

Duration of Response (DOR): The DOR is defined as the time from the date of the first documentation of the confirmed CR or PR (whichever occurs first) to the date of the disease progression objectively documented or death (whichever occurs first). If a subject had no record of disease progression or did not die before the data cut-off date, then the subject will be censored at the last available tumor assessment. The distribution of DOR will be estimated using Kaplan–Meier Method. Median duration of response and 95% CI will be provided.

5.4.4 Exploratory Efficacy Analysis

The efficacy tumor response endpoints (eg, PR, CR, SD and PD) will be explored based on modified RECIST 1.1 and RECIST 1.1 assessments. Same as the irRECIST, (1) a confirmation of complete responses or partial responses is required; (2) all tumor assessments as long as the subjects did not start a new anti-cancer therapy should be considered; (3) if there are more than 1 consecutive missing tumor assessments, all assessments afterward should not be considered for the determination of BOR (also see [Section 5.4.3](#) for PFS). However, different from irRECIST, a pseudoprogression is considered as a PD per the modified RECIST 1.1 and RECIST 1.1. Therefore, following the modified RECIST 1.1 and RECIST 1.1, any further tumor response assessments after the initial PD are not considered to determine BOR. For programming, only the tumor response data collected via the CRF of the modified RECIST 1.1 will be used. The general rules in the derivation of BOR with two consecutive tumor response results following the modified RECIST 1.1 and RECIST 1.1 are described in Table

7.

Table 7 General Rules Deriving BOR per modified RECIST 1.1 and RECIST 1.1

Timepoint 1 Overall Response	Timepoint 2 (\geq 4 weeks since Timepoint 1) Overall Response	BOR
CR	CR	CR
CR	PR	SD if duration of SD \geq 5 weeks, otherwise PD
CR	SD	SD if duration of SD \geq 5 weeks, otherwise PD
CR	PD	SD if duration of SD \geq 5 weeks, otherwise PD
CR	NE	SD if duration of SD \geq 5 weeks, otherwise NE. In the special case, if CR is after NE, BOR will be CR.
CR ^a		SD if duration of SD \geq 5 weeks, otherwise NE
PR	CR ^b	PR
PR	PR	PR
PR	SD	SD. In the special case if PR or CR is after SD, BOR will be PR.
PR	PD	SD if duration of SD \geq 5 weeks, otherwise PD
PR	NE	SD if duration of SD \geq 5 weeks, otherwise NE. In the special case, if PR or CR is after NE, BOR will be PR.
PR ^a		SD if duration of SD \geq 5 weeks, otherwise NE
SD	CR ^b	SD
SD	PR ^b	SD
SD	SD	SD
SD	PD	SD if duration of SD \geq 5 weeks, otherwise PD
SD	NE	SD if duration of SD \geq 5 weeks, otherwise NE
SD ^a		SD if duration of SD \geq 5 weeks, otherwise NE
PD ^c		PD
NE	NE	NE

UNK	UNK	UNK (Unknown) if there was no a baseline tumor assessment.
-----	-----	--

^a If this was the only tumor response assessment (e.g. study treatment was discontinued).

^b The subjects should be followed for ≥ 4 weeks to confirm the CR/PR.

^c There is no need to confirm this PD per the modified RECIST 1.1 and RECIST 1.1 (e.g. pseudo-progressions is considered as a PD).

5.4.5 Other Efficacy Analyses

No other efficacy analyses are planned for this study.

5.5 Pharmacokinetic, Pharmacodynamic, Pharmacogenomic and Other Biomarker Analyses

5.5.1 Pharmacokinetic Analyses

To assess any drug-drug interaction between lenvatinib and pembrolizumab, the dose-normalized PK profile for lenvatinib in combination with pembrolizumab from this study will be compared graphically to that from patients with different types of tumor from completed studies receiving lenvatinib monotherapy. PK analyses will be performed on Pharmacokinetic Analysis Set. Scatter plot, box plot and descriptive statistics including n, mean, SD, percent coefficient of variation (% CV), geometric mean, median, minimum and maximum will be used to summarize lenvatinib concentration data. All PK data, which include the complete bioanalytical results, time and date of blood draws and study drug administration, will be presented in subject-by-subject listings.

5.5.2 Pharmacodynamic, Pharmacogenomic and Other Biomarker Analyses

The effect of lenvatinib-pembrolizumab combination therapy on soluble, tissue, genetic and/or imaging biomarkers will be summarized using descriptive statistics using the pharmacodynamic analysis set. A separate analysis plan will be developed for the biomarker analyses, and results will be reported separately.

5.6 Safety Analyses

All safety analyses will be performed on the Safety Analysis Set. Safety data, will be presented using descriptive statistics (e.g., n, mean, SD, median, Q1, Q3, minimum, maximum) for continuous variables; n (%) for categorical variables). Safety variables include treatment-

emergent adverse events (TEAEs), clinical laboratory parameters, vital signs, 12-lead ECG results, and echocardiogram results including LVEF.

5.6.1 Extent of Exposure

Summary will be provided for duration of treatment, total dose per subject, dose intensity, relative dose intensity (received dose as percentage of planned dose per subject). All parameters for extent of exposure will be computed separately for lenvatinib and pembrolizumab.

The end date for lenvatinib will be imputed to the analysis cut-off date if the subject is still on treatment at the time of the data cut-off, and the dose will be imputed with the last dose recorded in the database for that subject. Duration of lenvatinib or pembrolizumab treatment is calculated as date of last dose – date of first dose + 1. Overall duration of treatment is defined as the duration between the earliest first dose start date of either medication and the latest last dose end date of either medication. For lenvatinib, total dose per subject, dose intensity (mg/day/subject), and received dose as percentage of planned dose per subject (Calculated as cumulative total dose divided by (planned starting daily dose x treatment duration in days)) will be summarized. Total (cumulative) dose per subject (mg) is defined as the sum of all doses actually taken by the subject. For pembrolizumab, dose Intensity (mg/IV administration) of pembrolizumab = Total dose received during the study/total number of IV administrations.

Number of subjects with dose reductions, dose interruptions, and time to first dose reduction will be summarized by counts and percent according to dose data.

To determine dose reduction and dose interruption, the incorrect doses that were taken by mistake should not be considered. Dose reduction refers to the situation that a dose level was reduced from the previous dose level without going back. Dose reduction is only applicable to lenvatinib, but not for Pembrolizumab as Pembrolizumab dose is always 200mg if it is administered. As an example below, the subject had two dose reductions on Day 4 and Day 6.

Obs	Subject Identifier	Treatment	Dose per Administration	Study Day of Start of Treatment	Study Day of End of Treatment
1	1001-10xx	LENVATINIB	20	1	2

2	1001-10xx	LENVATINIB	0	3	3
3	1001-10xx	LENVATINIB	14	4	5
4	1001-10xx	LENVATINIB	8	6	21
5	1001-10xx	LENVATINIB	8	22	50

Dose interruption for lenvatinib is defined as follow. The maximum days of dose interruptions is the duration of the longest interruption.

- Only include the scenario that the before and after dose 0 (interruption period), the dose levels are the same. For example: 24 mg followed by 0 mg and followed by 24 mg; 20 mg followed by 0 mg followed by 20 mg.
- If dose level reduces from previous dose level after dose interruption period (dose 0), it should be counted into dose reduction, but not dose interruption. For example, 24 mg followed by 0 mg followed by 20 mg, the period with 0 mg should not be counted into dose interruption.
- If after dose 0 mg, the subject discontinued from treatment permanently, it should be counted as a treatment discontinuation instead of a dose interruption.

For Pembrolizumab, as long as a dose was administered for a cycle, then there is no an interruption for this cycle.

Number of subjects with drug discontinuations due to AEs will be summarized by frequency counts and percentages.

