Q2W (KN001 Cohort B2, KN001 Cohort D, KN002, KN010, and KN021), and 3 studies compared 10 mg/kg Q3W versus 10 mg/kg Q2W (KN001 Cohort B3, KN001 Cohort F2 and KN006). All of these studies demonstrated flat dose- and exposure-response relationships across the doses studied representing an approximate 5- to 7.5-fold difference in exposure. The 2 mg/kg (or 200 mg fixed-dose) Q3W provided similar responses to the highest doses studied. Subsequently, flat dose-exposure-response relationships were also observed in other tumor types including head and neck cancer, bladder cancer, gastric cancer and classical Hodgkin Lymphoma, confirming 200 mg Q3W as the appropriate dose independent of the tumor type. These findings are consistent with the mechanism of action of pembrolizumab, which acts by interaction with immune cells, and not via direct binding to cancer cells.

Additionally, pharmacology data clearly show target saturation at 200 mg Q3W. First, PK data in KN001 evaluating target-mediated drug disposition conclusively demonstrated saturation of PD-1 in systemic circulation at doses much lower than 200 mg Q3W. Second, a physiologically-based PK analysis was conducted to predict tumor PD-1 saturation over a wide range of tumor penetration and PD-1 expression. This evaluation concluded that pembrolizumab at 200 mg Q3W achieves full PD-1 saturation in both blood and tumor.

Finally, population PK analysis of pembrolizumab, which characterized the influence of body weight and other participant covariates on exposure, has shown that the fixed dosing provides similar control of PK variability as weight-based dosing, with considerable overlap in the distribution of exposures from the 200 mg Q3W fixed dose and 2 mg/kg Q3W dose. Supported by these PK characteristics, and given that fixed-dose has advantages of reduced dosing complexity and reduced potential of dosing errors, the 200 mg Q3W fixed dose was selected for evaluation across all pembrolizumab protocols.

No dose reduction is allowed for pembrolizumab in this study.

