9.4.1.2 Pembrolizumab

Pembrolizumab (200 mg) will be administered as a 30-minute IV infusion, Q3W (infusions lasting between 25 minutes to 40 minutes are acceptable). The Pharmacy Manual contains specific instructions for the preparation of the pembrolizumab infusion and administration of infusion solution.

Subjects should maintain a normal diet unless modifications are required to manage an AE such as diarrhea, nausea or vomiting.

Study treatment with pembrolizumab may be administered up to 3 days before or after the scheduled D1 of each cycle due to administrative reasons.

Adverse events (both nonserious and serious) associated with pembrolizumab exposure may represent an immunologic etiology. These AEs may occur shortly after the first dose or several months after the last dose of treatment. Pembrolizumab must be withheld for drug-related toxicities and severe or life-threatening AEs as per [Table 4](#) below. See [Section 9.4.1.2.1](#) for supportive care guidelines, including use of corticosteroids.

Table 4 Dose Modification and Toxicity Management Guidelines for Immune-related Adverse Events Associated with Pembrolizumab

Immune-related Adverse Event	Toxicity Grade (CTCAE v4.0)	Action with Pembrolizumab	Corticosteroids and/or Other Therapies	Monitoring and Follow-up

General instructions:
 
 Severe and life-threatening irAEs should be treated with IV corticosteroids followed by oral steroids. Other immunosuppressive treatment should begin if the irAEs are not controlled by corticosteroids. Pembrolizumab must be permanently discontinued if the irAE does not resolve or the corticosteroid dose is not ≤ 10 mg/day within 12 weeks of the last pembrolizumab-treatment. The corticosteroid taper should begin when the irAE is \leq Grade 1 and continue at least 4 weeks. 
If pembrolizumab has been withheld, pembrolizumab may resume after the irAE decreased to \leq Grade 1 after corticosteroid taper.
				
Pneumonitis	Grade 2	Withhold	Administer corticosteroids (initial dose of 1 to 2 mg/kg prednisone or equivalent) followed by taper. Add prophylactic antibiotics for opportunistic infections.	Monitor participants for signs and symptoms of pneumonitis. Evaluate participants with suspected pneumonitis with radiographic imaging and initiate corticosteroid treatment.
	Recurrent Grade 2, 3 or 4	Permanently discontinue		

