Dosing interruptions are permitted in the case of medical/surgical events or logistical reasons not related to study therapy (eg, elective surgery, unrelated medical events, subject vacation, and/or holidays). Subjects should be placed back on study treatment within 3 weeks of the scheduled interruption, unless otherwise discussed with the sponsor. The reason for interruption should be documented in the subject's study record.

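### The SAP's pembrolizumab dose intensity is 200 mg for every subject by construction, so that line says nothing about held, delayed or omitted infusions

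*SAP*

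**What the plan says.** SAP Section 5.6.1 gives this rule: "For pembrolizumab, dose Intensity (mg/IV administration) of pembrolizumab = Total dose received during the study/total number of IV administrations". The same section explains why dose reductions are not tabulated for this drug: "Dose reduction is only applicable to lenvatinib, but not for Pembrolizumab as Pembrolizumab dose is always 200mg if it is administered". Protocol Section 7.2 agrees: "No dose reduction is allowed for pembrolizumab in this study".

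The planned schedule is in Protocol Section 9.4.1.2: "Pembrolizumab (200 mg) will be administered as a 30-minute IV infusion, Q3W". That section also expects departures from it. On toxicity: "Pembrolizumab must be withheld for drug-related toxicities and severe or life-threatening AEs". On other causes: "Dosing interruptions are permitted in the case of medical/surgical events or logistical reasons not related to study therapy".

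For lenvatinib, SAP 5.6.1 uses mg per day, plus cumulative dose over planned starting daily dose times treatment days. Its opening paragraph promises relative dose intensity, described in words as received dose as a percentage of planned dose, and says all exposure parameters are computed for each drug separately. No planned-dose denominator is written for pembrolizumab. The interruption rule is: "For Pembrolizumab, as long as a dose was administered for a cycle, then there is no an interruption for this cycle".

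**The concern.** A dose-intensity measure should fall when less drug is delivered than planned. Because the dose per infusion is fixed, pembrolizumab delivery falls mainly through infusions that are held, given late, omitted or stopped, and neither time nor planned dose enters the SAP formula. Tolerability of the combination is a secondary objective. A line showing 200 mg in every cohort, printed beside a time-based lenvatinib figure, could be misread as full delivery of pembrolizumab.

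**Working it through.** **Inputs.** Dose per infusion 200 mg, no reductions (SAP 5.6.1; Protocol 7.2). Interval 21 days (Protocol 9.4.1.2). Maximum 35 infusions (Protocol 9.1). SAP treatment duration = last dose date − first dose date + 1 (SAP 5.6.1). The dosing histories below are assumed for illustration and are not trial data.

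**The plan's own figure.** Dose intensity = (n × 200)/n = 200 mg per administration for any n ≥ 1, which reproduces the SAP's constant dose. One incomplete infusion of 100 mg among eight gives (7 × 200 + 100)/8 = 187.5 mg. The measure can register that, but it is not a hold, delay or omission.

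**Comparison.** Two other measures are set beside it:
- mg per 3 weeks = total dose / [(last − first + 21)/21]
- percent of plan = total dose / (200 × infusions planned)

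| History | Total mg | SAP formula | mg per 3 weeks | Percent of plan |
|---|---|---|---|---|
| 8 of 8 on schedule | 1600 | 1600/8 = 200 | (147+21)/21 = 8; 1600/8 = 200 | 1600/1600 = 100% |
| Cycles 3, 4, 6 of 8 omitted | 1000 | 1000/5 = 200 | 8 intervals; 1000/8 = 125 | 1000/1600 = 62.5% |
| Only Cycles 1, 3, 5, 7 of 8 | 800 | 800/4 = 200 | (126+21)/21 = 7; 800/7 = 114 | 800/1600 = 50% |
| 8 infusions, every 28 days | 1600 | 1600/8 = 200 | (196+21)/21 = 10.33; 1600/10.33 = 155 | 1600/2000 = 80% |
| Held after Cycle 3, plan running to Cycle 8 | 600 | 600/3 = 200 | (42+21)/21 = 3; 600/3 = 200 | 600/1600 = 37.5% |

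The SAP column never changes. In the last row, mg per 3 weeks also stays at 200, because its interval closes 21 days after the last infusion given. It cannot serve as the relative measure on its own.

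**Late within a cycle.** Take the first three infusions of the 28-day history, on Days 1, 29 and 57. On a fixed 21-day calendar, Cycles 2 and 3 start on Days 22 and 43, so the infusions are 7 and 14 days late. Each still falls in its own cycle, so no interruption is counted. Delivery is 600/[(56+21)/21] = 600/3.67 = 164 mg per 3 weeks, or 82% of 200.

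**Borrowing the lenvatinib formula.** At a planned 200/21 mg per day, a fully compliant 8-infusion subject has 148 treatment days: 1600/(148 × 200/21) = about 114%. A one-infusion subject has 1 day: 200/(200/21) = 2100%. The lenvatinib denominator therefore does not carry over to a drug given every 3 weeks.

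**The case against.** A reader might infer that the SAP cannot show missed pembrolizumab at all, or that its tables would lead people to conclude that lenvatinib did not compromise pembrolizumab delivery. The documents do not support that. SAP 5.6.1 also plans total dose, duration, counts of subjects with interruptions, and discontinuations due to adverse events. The interruption rule works per cycle, so a cycle with no infusion can register. SAP 5.6.3 tabulates adverse events leading to interruption and to discontinuation. Protocol 9.7.1.8.1 adds cycles on treatment and quantity administered. The subject dosed only in Cycles 1, 3, 5 and 7 would show up through the empty cycles and an 800 mg total. The measure is also labelled per IV administration, so it does not claim to be a rate over time. All of this stands, and it limits the point.

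Derivation rules and table shells sit in separate documents (SAP Sections 9 and 11), which may hold a relative dose intensity formula for pembrolizumab. That is possible. It does not rescue the dose-intensity formula, which the SAP states outright.

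It also stands that exposure falls through permanent discontinuation as well as through holds and delays, and that discontinuation is tabulated separately.

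**Conclusion.** The point holds for the dose-intensity line: "Pembrolizumab dose is always 200mg if it is administered" makes it a constant, apart from a partial infusion or a dosing error. In the assumed histories it reads 200 mg while the share of planned drug delivered runs from 100% down to 37.5%. Two smaller gaps go with it. An infusion given late within its cycle is not counted as an interruption, and the relative dose intensity promised for both drugs has no workable pembrolizumab formula in the SAP. Skipped cycles remain visible elsewhere. The effect is on descriptive exposure reporting only; no efficacy endpoint is touched. The arithmetic rests on the fixed 200 mg dose and the 3-week schedule; how often infusions were actually held or late is not known from these documents.

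**What to change.** In SAP 5.6.1, replace the pembrolizumab formula and add the missing one:

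- Dose intensity (mg per 3 weeks) = total dose / [(last infusion date − first infusion date + 21)/21].
- Relative dose intensity = total dose / (200 mg × number of 3-weekly infusions planned up to the date pembrolizumab was permanently discontinued or the data cutoff, capped at 35).

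The first shows lateness and gaps between infusions. The second also counts infusions held after the last one given. The SAP should name the source of the discontinuation date. If the last infusion date is used instead, the history held after Cycle 3 returns to 600/600 = 100%.

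Keep total dose and number of infusions, and present the result beside the discontinuation counts, because infusions after permanent discontinuation are outside the denominator. The cost is one SAP sentence and one or two re-derived variables. Infusion dates are already needed for treatment duration.
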